11.3.9. Time Point response

A summary of the overall response status calculation at each time point for patients who have measurable disease at baseline is presented in Table A1 below.

11.3.10. Table A1. Time point response: Patients with target (+/-non-target) disease

Target lesions	Non-Target lesions	New Lesions	Overall response
CR	CR	No	CR
CR	Non-CR/non-PD	No	PR
CR	NE	No	PR
PR	Non-PD/or not all evaluated	No	PR
SD	Non-PD/or not all evaluated	No	SD
Not all evaluated	Non-PD	No	NE
PD	Any	Yes or No	PD
Any	PD	Yes or No	PD

Any	Any	Yes	PD
-----	-----	-----	----

CR = complete response; PR = partial response; SD = stable disease; PD = progressive disease; NE = inevaluable.

When patients have non-measurable (therefore non-target) disease only, Table A2 is to be used.

11.3.11. Table A2. Time point response: Patients with non-target disease

Non-Target lesions	New Lesions	Overall response
CR	No	CR
Non-CR/non-PD	No	Non-CR/non-PD ¹
Not all evaluated	No	NE
PD	Yes or No	PD
Unequivocal PD	Yes or No	PD
Any	Yes	PD

CR = complete response; PR = partial response; SD = stable disease; PD = progressive disease; NE = inevaluable.

¹ Non-CR / non-PD is preferred over 'Stable Disease' for non-target disease since SD is increasingly used as an endpoint for assessment of efficacy in some trials. To assign this category when no lesions can be measured is not advised

11.3.12. Confirmation

In non-randomized trials where response is the primary endpoint, confirmation of PR and CR is required to ensure responses identified are not the result of measurement error. This will also permit appropriate interpretation of results in the context of historical data where response has traditionally required confirmation in such trials.

However, in all other circumstances, (i.e., in randomized phase II or III trials or studies where stable disease or progression are the primary endpoints), confirmation of response is not required since it will not add value to the interpretation of trial results. However, elimination of the requirement for response confirmation may increase the importance of central review to protect against bias, in particular in studies, which are not blinded.

In the case of SD, measurements must have met the SD criteria at least once after study entry at a minimum interval (in general not less than 6–8 weeks) that is defined in the study protocol.

11.3.13. Missing Assessments and Inevaluable Designation

When no imaging/measurement is done at all at a particular time point, the patient is not evaluable (NE) at that time point.

If only a subset of lesion measurements are made at an assessment, usually the case is also considered NE at that time point, unless a convincing argument can be made that the contribution of the individual missing lesion(s) would not change the assigned time point response. This would most likely happen in the case of PD.

11.4. Appendix 4 National Cancer Institute Common Terminology Criteria for Adverse Events (NCI CTCAE) Version 5.0

The NCI CTCAE Version 5.0 can be found by going to the following web site:

<http://ctep.cancer.gov/reporting/ctc.html>

Inquiries specifically regarding the Common Toxicity Criteria (CTC) should be addressed to:

[contact]

3 LIST OF ABBREVIATIONS AND DEFINITIONS OF TERMS

AE	adverse event
ATC	Anatomic Therapeutic Chemical
BMI	body mass index
CA125	cancer antigen 125
CA19-9	cancer antigen 19-9
CEA	carcinoembryonic antigen
CFB	change from baseline
CI	confidence interval
CR	complete response
eCRF	electronic case report form
CT	computed tomography
CTCAE	Common Terminology Criteria for Adverse Events
DBP	diastolic blood pressure
DSMC	Data and Safety Monitoring Committee
ECOG	Eastern Cooperative Group
EDC	electronic data capturing
EFFS	Efficacy Analysis Set
FAP	fibroblast activation protein
FAPI	fibroblast-activation-protein inhibitors
FDA	Food and Drug Administration
FDG	fluorodeoxyglucose
GCP	good clinical practice
ICH	International Council for Harmonisation
IHC	immunohistochemistry
MedDRA	Medical Dictionary for Regulatory Activities
MRI	magnetic resonance imaging
NAT	neoadjuvant therapy (chemotherapy, radiation therapy, or both)
NPV	negative predictive value
PD	protocol deviation(s)

PDAC	pancreatic ductal adenocarcinoma
PET	positron emission tomography
PG	performance goal
PPV	positive predictive value
PPS	Per protocol analysis set
PR	partial response
PT	preferred term
SAE	serious adverse event
SAP	statistical analysis plan
SAS	Safety analysis set
SBP	systolic blood pressure
SD	standard deviation
SOC	system organ class
SUV	standardized uptake value
SUV _{max}	maximum standardized uptake value
SUV _{mean}	mean standardized uptake value
TBR	tumor to background ratio
TEAE	treatment emergent adverse event
TESAE	treatment emergent serious adverse event
TLF	tables, listings, and figures
WHO	World Health Organization

4 INTRODUCTION

The purpose of this SAP is to describe the framework for the reporting, summarization, and statistical analysis methodology of the safety and efficacy parameters measured throughout the study. It is based on Protocol GaFAPI-2022P2, Version 5.0 dated 31 Mar 2023.

5 STUDY OBJECTIVES AND ENDPOINTS

5.1 Objectives and Endpoints

Table 1. Objectives and Endpoints

Objectives	Endpoints
Primary	
To evaluate the performance of [⁶⁸ Ga]FAPI-46 PET ^a imaging to detect FAP-expressing cells, using histopathology as truth standard.	Sensitivity to detect PDAC will be determined on a per-patient basis. Primary lesion confirmed as positive by histopathology and assessed as positive by the blinded reader will be considered as True Positive (TP). Primary lesion confirmed as positive by histopathology and but not identified by the blinded reader will be considered as False Negative (FN). Sensitivity will be calculated as: TP / (TP + FN).
Secondary	
To correlate the histopathology with FAP staining on FAP IHC assay.	
Staining intensity assessed by IHC, using H-score, correlated to the uptake of [⁶⁸Ga]FAPI-46, using SUV_{max}
 
 Lesions positive for FAP as detected by IHC with available SUV_{max} 
Note: SUV_{mean} will also be compared to IHC H-score for exploratory purposes.

To further characterize the safety profile of [⁶⁸ Ga]FAPI-46 in patients with PDAC.	Incidence and severity of TEAEs or TSEAEs according to MedDRA/CTCAE V.5.0
Exploratory	
To compare the detection of local and metastatic disease using [⁶⁸ Ga]FAPI-46 PET to a composite of clinical, radiological (ie, CT, MRI) in patients with resectable or borderline resectable PDAC.	
Number of lesions identified through Standard of Care (anatomical (ie, CT, MRI) and/or [¹⁸F]-FDG PET) and [⁶⁸Ga]FAPI-46 PET images
 
Radiotracer accumulation observed in identified lesions using SUV

To compare pre and post treatment [⁶⁸ Ga]FAPI-46 PET evaluations obtained in Cohort 2 to identify perturbations, if any, from neoadjuvant therapy treatment.	Percentage change in [⁶⁸ Ga]FAPI-46 PET imaging using SUV levels in the primary lesion between pre- and post-neoadjuvant therapy

Abbreviations: CT = computed tomography; CTCAE = Common Terminology Criteria for Adverse Events; FAP = fibroblast activation protein; FAPI = fibroblast-activation-protein inhibitors; FDG = fluorodeoxyglucose; IHC = immunohistochemistry; MedDRA = Medical Dictionary for Regulatory Activities; MRI = magnetic resonance imaging; PDAC = pancreatic ductal adenocarcinoma; PET = positron emission tomography; SUV = standardized

uptake value; SUV_{max} = maximum standardized uptake value; TEAE = treatment-emergent adverse event; TESAE = treatment-emergent serious adverse event

5.2 Estimands

The estimand approach for the primary and secondary endpoints is presented in [Table 2](#).

Table 2. Endpoints and Estimands

Endpoint	Estimand
Primary	
Per patient Sensitivity to detect PDAC using histopathology as truth standard.	
a) Population: EFFS1
 
b) Endpoint: Positive/Negative status according to ⁶⁸Ga]FAPI-46 PET and Positive/Negative status according to histopathology (See Table 10) for the primary lesion
 
c) Intercurrent event(s): There are no intercurrent events prespecified.
 
d) Population level summary measure^a:
 
 Sensitivity: point estimate, SE, 90% asymptotic normal CI and p-value
Secondary	
H-score correlated to the uptake of ⁶⁸ Ga]FAPI-46, using SUV _{max} .	
a) Population: EFFS2
 
b) Endpoint: SUV_{max} and H-score^b
 
c) Intercurrent event(s): There are no intercurrent events prespecified.
 
d) Population level summary measure: Spearman correlation coefficient and 95% CI

Incidence and severity of TEAEs or TESAEs	
Note: In addition, sensitivity and specificity of ⁶⁸Ga]FAPI-46 PET to detect FAP-expressing cells using H-score as standard of truth will be presented.
 
a) Population: SAS
 
b) Endpoint: Incidence of AEs
 
c) Intercurrent event(s): There are no intercurrent events prespecified.
 
d) Population level summary measure: Frequency and percentages of patients with each type of TEAE in each cohort.
 
 TEAEs Serious TEAEs TEAEs by maximum severity Study drug-related TEAEs Fatal TEAEs

Abbreviations: AE = adverse event; CI = confidence interval; CT = computed tomography; Efficacy analysis set; FAP = fibroblast activation protein; FAPI = fibroblast-activation-protein inhibitors; FDG = fluorodeoxyglucose; IHC = immunohistochemistry; NPV = negative predictive value; PDAC = pancreatic ductal adenocarcinoma; PET = positron emission tomography; PPV = positive predictive value; SAS = Safety analysis set; SE = standard error; SUV = standardized uptake value; SUV_{max} = maximum standardized uptake value; TEAE = treatment emergent adverse event; TESAE = treatment emergent serious adverse event

- a The primary focus will be on the 90% confidence interval CI to align with the 5% one-sided test; however, the 95% asymptotic normal confidence interval will also be presented for descriptive purposes.
- b SUV_{mean} will also be compared to IHC H-score for exploratory purposes.

6 STUDY DESIGN CONSIDERATIONS

6.1 Study Design

This is a prospective, multi-center, single arm, open label, non-randomized study to evaluate the ability of [⁶⁸Ga]FAPI-46 to detect FAP expressing cells in patients with resectable or borderline resectable PDAC. The [⁶⁸Ga]FAPI-46 PET scans were acquired after initial staging using institutional standard methods. If the participant was prescribed NAT, a second [⁶⁸Ga]FAPI-46 PET scan was performed within 21 days prior to planned surgical resection. This was followed by histopathology and IHC analyses and comparison to resected PDAC tumor specimens. The surgeon was not blinded to the [⁶⁸Ga]FAPI-46 scans prior to surgery.

[figure not shown]
Experimental Design: Phase 2, prospective, multi-center, single arm, non-randomized, open label study

Allocation of treatment: open-label, non-randomized, single intervention

Number of patients planned: Up to 60 patients enrolled.

Summary of Study Visits and Data Collection: Refer to Schedule of Events ([Table 5](#)) for full requirements for each visit. The Schema ([Figure 1](#)) provides a graphical representation of the study visits.

Figure 1. Schema

Abbreviations: CT = computed tomography; FAPI = fibroblast-activation-protein inhibitors; FDG = fluorodeoxyglucose; hrs = hours; PDAC = pancreatic ductal adenocarcinoma; PET = positron emission tomography

All participants

Screening: Screening assessments could be conducted at multiple visits provided they are within 28 days prior to study day 1, including anatomic imaging. Tests performed for standard of care were permitted to be used for screening purposes provided they were within window.

Visit 1: Defines Study Day 1. [⁶⁸Ga]FAPI-46 PET scan obtained.

Visit 2: 24 to 72 hours after [⁶⁸Ga]FAPI-46 injection. Safety assessment with safety labs and, if needed, a symptom directed physical examination. This was the last active study-related event with the participant.

Cohort 1 only:

Participants in Cohort 1 were those not prescribed NAT who directly underwent surgical resection within 21 days post-[⁶⁸Ga]FAPI-46 PET scan. Data were mined from the medical records regarding the surgical procedure and pathologic outcomes. The final study-directed visit is Visit 2.

Surgery: Surgical resection occurred within 21 days after [⁶⁸Ga]FAPI-46 PET scan. Resected tissue was collected as per laboratory manual. Surgical and pathology reports were collected, codified, and provided for study.

Follow-up: Passive follow-up only through chart review to collect information about post-surgical imaging, planned treatment, and outcomes for 14 days following surgery.

Cohort 2 only:

Participants in Cohort 2 were those who received a tumor biopsy and who were prescribed NAT followed by surgical resection within 21 days after a second [⁶⁸Ga]FAPI-46 PET scan. NAT was beyond the scope of this protocol and was to be administered per standard of care by the institution and treating oncology team. Data were mined from the medical records regarding the NAT administered, surgical procedure and pathologic outcomes. The final study-directed visit was Visit 4.

Visit 3: Second [⁶⁸Ga]FAPI-46 PET scan.

Visit 4: 24 to 72 hours after [⁶⁸Ga]FAPI-46 injection. Safety assessment with safety labs and, if needed, a symptom directed physical examination.

Surgery: Surgical resection occurred within 21 days after [⁶⁸Ga]FAPI-46 PET scan. Resected tissue was collected as per laboratory manual. Surgical and pathology reports were collected.

Follow-up: Passive follow-up only through chart review to collect information about post-surgical imaging, planned treatment, and outcomes for 14 days following surgery.

6.1.1 Safety Review Committee / Data Monitoring Committee

This Phase 2 imaging trial was not considered to have a safety risk or toxicity, thus not meeting any of the FDA criteria highlighted in the DSMC charter. Additionally, the trial had a small accrual goal (n = 60) with a targeted completion of less than 1 year and is in an early stage to determine the efficacy of [⁶⁸Ga]FAPI-46 in identifying pancreatic adenocarcinoma. Thus, a DSMC was not convened as it would not have ameliorated safety risk to participants, it would not have functioned to assess futility, and it would not have overseen unblinded data.

However, the sponsor concurred that independent oversight was critical to protect the rights, safety, and welfare of study participants as well as to ensure scientifically valid data. For this purpose, the sponsor established the necessary independent organizations and individuals.

6.1.2 Justification of Sample Size

The sample size is 60 patients in order to adequately power the primary objective of sensitivity.

For this study, the primary efficacy endpoints is sensitivity, evaluated with a hypothesis test:

H0: Sensitivity \leq PG

H1: Sensitivity $>$ PG

The minimum sample size necessary to achieve power for sensitivity was computed for the hypothesis test above utilizing a one-sample binomial proportion test with a normal approximation, an upper one-sided significance level of 0.05, and the following parametric assumptions:

- PG = 0.75 for sensitivity
- True Sensitivity = 0.90

Given the parametric assumptions above, 60 patients yields 92.7% power to demonstrate that the true sensitivity is greater than 0.75.

6.2 Efficacy Measures

Refer to [Section 10.6](#) for a complete description of the efficacy analyses.

Only the primary tumor and a maximum of three lymph nodes will be considered for analysis and handled based on the available information.

6.2.1 Primary Efficacy Measures

The primary efficacy endpoints will be defined based on a [⁶⁸Ga]FAPI-46 PET image result (positive or negative) and a histopathology result (positive and negative) at patient level. Imaging data reads were conducted by a single reader at a central image reading lab followed by quantitative recording of PET image SUV data. The primary tumor and up to a maximum of three lymph nodes were assessed by the central lab and only those lesions that have both imaging and histopathology results will be used for primary endpoint calculation.

For the primary analysis, sensitivity will be determined based on a single tissue sample from biopsied or resected specimens collected from the primary tumor

Refer to [Table 10](#) to determine positive imaging and histopathology results.

6.2.2 Secondary Efficacy Measures

The secondary efficacy endpoint will compare the results from [⁶⁸Ga]FAPI-46 PET and IHC using:

The secondary efficacy endpoints to be analyzed include:

- Correlation between SUV_{max} and H-score
- Correlation between SUV_{mean} and H-score

Besides, the sensitivity and specificity of [⁶⁸Ga]FAPI-46 PET to detect FAP-expressing cells using H-score as SoT will be tabulated. Refer to [Table 10](#) to determine positive imaging and IHC results.

6.2.3 Exploratory Efficacy Measures

The exploratory endpoints to be analyzed include:

- Number of lesions identified (0, 1, 2, 3 or more) through Standard of Care (anatomical (ie, CT, MR) and/or [¹⁸F]-FDG PET) and [⁶⁸Ga]FAPI-46 images
- Radiotracer accumulation observed in identified lesions SUV_{max}, SUV_{mean}, and tumor-to-background ratio (TBR) . If different background regions (such as muscle, blood, etc...) are used, TBR will be calculated and presented for all of them.
- Percentage change in [⁶⁸Ga]FAPI-46 PET SUV_{max} in the primary lesion between pre- and post-neoadjuvant therapy

6.3 Safety Measures

All patients who receive any amount of [⁶⁸Ga]FAPI-46 will be included in the final summaries and listings of safety data.

The safety endpoints to be analyzed include:

- Any reported TEAE
- Any Serious TEAE
- TEAEs by maximum severity grade
- Any Study drug related TEAE
- Any Fatal TEAE
- Clinical laboratory results, including hematology and serum chemistry
- Vital signs, including body temperature, respiratory rate, SBP, DBP, and heart rate
- Physical examination results

6.4 Pharmacokinetic Measures/Parameters

Not applicable.

6.5 Pharmacodynamic Measures/Parameters

Samples of serum for CA19-9 (or CA125, CEA if non-secretors for pancreas cancer), CEA and CA125 as applicable, any tumor marker appropriate to the given cancer or that is known to be elevated in each patient, were collected and processed as per the instructions provided in the respective laboratory manuals. Serum tumor biomarkers levels were also determined as per the instructions provided in the respective lab manuals.

7 STUDY POPULATIONS

7.1 Analysis Populations

7.1.1 Safety Analysis Set (SAS)

All patients who received any amount of [⁶⁸Ga]FAPI-46. The SAS will be used for all safety evaluations.

7.1.2 Efficacy Analysis Sets

Patients with uninterpretable [⁶⁸Ga]FAPI-46 PET data will be excluded from the efficacy analyses. Number (%) of patients with uninterpretable [⁶⁸Ga]FAPI-46 PET images will be summarized. Uninterpretable image data is defined as a response of “No” to the eCRF question: “Is Image of technical quality for interpretation?”.

SUV values from [⁶⁸Ga]FAPI-46 PET imaging were only reported for regions judged positive by the blinded reader. Missing SUV values for the primary tumor within the transfer file, where the response in the EDC is interpretable (i.e., ‘Yes’ to the eCRF question: ‘Is the image of technical quality for interpretation?’), will be treated as a negative region.

Furthermore, patients with missing or invalid histopathology data (standard of truth) will be imputed as positive for the primary region of interest, in line with the study design, which requires all patients to be positive for PDAC to be eligible for inclusion.

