8. STATISTICAL ANALYSIS

8.1. General

Descriptive statistics will be utilized for safety parameters. All patients will be accounted for. The study population for all analyses will be defined as all patients enrolled in the study who receive at least one dose of [⁶⁸Ga]FAPI-46. Patients who exit the study prior to receiving study medication may be replaced.

For this study, the primary efficacy endpoints are sensitivity and specificity, each of which will be evaluated with a hypothesis test:

H_0 : Sensitivity (Specificity) \leq Performance Goal (PG)

H_1 : Sensitivity (Specificity) $>$ Performance Goal (PG)

Where success is defined as rejecting the null hypothesis for the sensitivity hypothesis tests. The specificity test will have lower power given the lower number of samples that are likely to be negative from the histopathology sample.

The minimum sample size necessary to achieve desired power for sensitivity was computed for the hypothesis test above utilizing a one-sample binomial proportion test with a normal approximation, an upper one-sided significance level of 0.05, and the following parametric assumptions:

- Performance Goal (PG) = 0.75 for sensitivity and 0.70 for specificity
- True Sensitivity and Specificity = 0.90

Given the parametric assumptions above, 60 subjects will yield 92.7% power to demonstrate that the true sensitivity and specificity is greater than 0.75.

Additional exploratory data analyses will be conducted as deemed appropriate by the Sponsor.

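### Dosed patients with uninterpretable scans leave the primary sensitivity analysis, although the protocol's population is all dosed patients; SAP Section 8 does not list the change, and no efficacy analysis includes them.

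*SAP*

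**What the plan says.** Protocol 8.1 sets one population: "The study population for all analyses will be defined as all patients enrolled in the study who receive at least one dose" of FAPI-46. It makes no exception for image quality. The protocol's primary endpoint (5.2.1) is restricted only by whether tissue is available.

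SAP 7.1.2 says that patients with uninterpretable FAPI-46 "PET data will be excluded from the efficacy analyses". A scan is uninterpretable when the case report form question on technical quality is answered No. EFFS1 (SAP 7.1.2.1) requires an interpretable scan with a matching histopathology result, and SAP 10.6.2 bases the primary analysis on EFFS1.

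Two related rules stand in SAP 7.1.2 and 9.4. A readable image with no SUV for the primary tumour is scored negative. Missing histopathology is scored positive, because eligibility requires confirmed PDAC.

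SAP Section 8 lists changes to the primary endpoint, the exploratory endpoints and the confidence level, but none to the analysis population. SAP Table 2 prespecifies no intercurrent events.

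The SAP does plan disclosure:
- the number and percentage of patients with uninterpretable images (7.1.2);
- a listing of reasons for exclusion (10.1);
- a summary and listing of image quality (10.5);
- a listing of PET and histopathology results for the safety set, with EFFS1 members flagged (10.6.2).

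**The concern.** Every eligible patient has confirmed PDAC. By the SAP's own reasoning on missing histopathology, a dosed patient with an unreadable scan is therefore disease-positive and would belong in the denominator A + C. Exclusion makes sensitivity conditional on a readable image, which is narrower than the protocol's stated population.

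One form entry decides which side of the line a patient falls on. A readable image with no SUV counts as a false negative, while an image marked uninterpretable leaves the denominator. The per-protocol set is a subset of EFFS1 (SAP 7.1.3), so no planned efficacy analysis brings these patients back.

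At stake is the success claim of a single-arm trial judged against a fixed goal of 0.75, where a difference of one or two patients can matter.

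**Working it through.** **Inputs (SAP 6.1.2).** The test is a "one-sample binomial proportion test with a normal approximation" at "an upper one-sided significance level of 0.05", with "PG = 0.75 for sensitivity" and "True Sensitivity = 0.90". The stated result is that "60 patients yields 92.7% power to demonstrate that the true sensitivity is greater than 0.75".

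**The plan's own figure.** With the null variance, z = (A/n − 0.75) / √(0.75 × 0.25 / n), and success needs z > 1.645. At n = 60 the smallest successful count is A = 51. The exact binomial probability of 51 or more of 60 is 92.7% at 0.90 and 4.5% at 0.75. The stated power reproduces, so the sample-size figure is not in question.

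**Assumptions for the comparison.** There are 60 scanned, histology-positive patients, of whom U have no interpretable scan. The documents give no value for U. I use 2 and 3 for the examples and 0 to 10 as the range. EFFS1 gives A/(60 − U). The worst case, with unreadable scans counted as not detected, gives A/60. Since 60 − U ≤ 60, the EFFS1 figure is never the lower of the two, and they are equal at U = 0.

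| U | A | EFFS1 | Worst case | Verdicts |
|---|---|---|---|---|
| 2 | 50 | 50/58 = 86.2%, z = 1.97, p = 0.024 | 50/60 = 83.3%, z = 1.49, p = 0.068 | differ |
| 3 | 49 | 49/57 = 86.0%, z = 1.91, p = 0.028 | 49/60 = 81.7%, z = 1.19, p = 0.117 | differ |
| 2 | 52 | 52/58 = 89.7%, z = 2.58, p = 0.005 | 52/60 = 86.7%, z = 2.09, p = 0.018 | both succeed |
| 3 | 51 | 51/57 = 89.5%, z = 2.52, p = 0.006 | 51/60 = 85.0%, z = 1.79, p = 0.037 | both succeed |

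**How often the verdicts differ.** EFFS1 needs 49 positives when n is 58 or 57, and the worst case needs 51 of 60. The verdicts therefore differ only at A = 49 or 50. With true sensitivity 0.90 among readable scans, the probabilities are:
- U = 2: 93.95% − 77.97% = 16.0%
- U = 3: 88.80% − 65.71% = 23.1%

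**Size of the shift.** At 0.90 among readable scans, the expected worst-case figure is 0.90 × (60 − U)/60. The gap is 0.90 × U/60, or 1.5 points per scan: 0 at U = 0, 3.0 points at U = 2, 4.5 at U = 3 and 15 at U = 10.

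**Chance of success at the goal.** Suppose sensitivity over all 60 is truly 0.75 and every unreadable scan is a non-detection. Sensitivity among readable scans is then 45/(60 − U). The chance of success under the SAP rule is 4.5% at U = 0, 8.0% at U = 1, 13.3% at U = 2 and 12.5% at U = 3.

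**The case against.** A reader might infer three stronger things, and the documents support none of them.

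*That exclusion can only inflate sensitivity.* The direction depends on scoring unreadable scans as not detected. The trigger is technical quality, not absent uptake. If technical failures are unrelated to uptake, exclusion is unbiased for sensitivity among readable scans, which is a legitimate quantity. Scoring them as positive would reverse the sign: with U = 2 and A = 50, 52/60 = 86.7% against 50/58 = 86.2%.

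*That the protocol counts unreadable scans as failures.* Its two-by-two table (8.3.1) has only PET-positive and PET-negative rows, its endpoint is already limited by tissue availability, and 8.7 refers to the SAP for the full plan. The protocol states an all-dosed population and gives no rule for unreadable scans.

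*That these patients disappear from the report.* The count and listings would let a careful reader rebuild the wider figure. What is missing is a planned analysis.

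It is also fair to say that the two rows with differing verdicts use the only counts where they can differ, that reads were central and blinded, and that scoring a readable image without an SUV as negative is conservative. In Cohort 2 an unreadable second scan need not lose the patient: SAP 10.6 speaks of a single readable scan, but 7.1.2.1 and 10.6 do not say clearly whether the first scan then serves.

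All of this limits the size and wording of the point. It does not remove the unlisted change of population or supply the missing analysis.

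**Conclusion.** The point holds in limited form. The SAP narrows the primary population from all dosed patients to those with an interpretable scan, does not list this in Section 8, and plans no efficacy analysis that includes the excluded patients.

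If unreadable scans count as not detected, the estimate rises by about 1.5 points per scan at 0.90, and the verdict can change when the positive count is borderline (49 or 50, for 2 or 3 unreadable scans). At an observed sensitivity near 0.90 with 2 or 3 such scans, the conclusion stands either way; with none there is no effect. The size rests on an assumed number of unreadable scans and on the worst-case scoring. Neither comes from the documents.

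**What to change.** 1. List the change of analysis population in SAP Section 8, with the reason.
2. Add to SAP 10.6.2, before database lock, a supportive worst-case analysis with the same test and confidence intervals. Its population is EFFS1 plus dosed patients who were scanned but have no interpretable FAPI-46 scan. Count the added patients as PET-negative and histology-positive, using the SAP's own imputation rule where histopathology is missing.
3. State that a Cohort 2 patient with an unreadable second scan and a readable first scan is analysed on the readable one.
4. Do not score scans that were never performed as negative. Otherwise a Cohort 2 patient with a positive first scan and no second scan could become a false negative for reasons unrelated to image quality.
5. Require the report to say if the two analyses disagree.

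The cost is one table and a few lines of text. The supportive figure will equal the primary one or fall below it. Its power at 0.90 among readable scans is also lower, at 78.0% for 2 unreadable scans and 65.7% for 3, so it should stay supportive and not become a second condition for success.

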7.1.2.1 Efficacy Analysis Set 1 (EFS1)

All patients in Cohort 1 who received [⁶⁸Ga]FAPI-46, with an interpretable (when answer to eCRF question: “Is Image of technical quality for interpretation?” is “Yes”) FAPI-46 PET image result (positive or negative) for at least 1 lesion with a corresponding histopathology result (positive or negative).

All patients in Cohort 2 who received [⁶⁸Ga]FAPI-46, with an interpretable FAPI-46 PET image result for at least 1 lesion with a corresponding histopathology result. For patients with multiple PET scans, only one PET scan will be considered for analysis. The most recent PET scan performed prior to surgery for patients with multiple scans will take precedence for analysis.

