9.4 Imputation and Handling of Partial Dates

Patients with missing or invalid histopathology data (the standard of truth) will be considered positive for the primary region of interest, in line with the study design, which requires all

patients to be positive for PDAC in order to be eligible for inclusion. Missing SUV values for the primary tumor, where the response in the EDC is interpretable (i.e., ‘Yes’ to the eCRF question: ‘Is the image of technical quality for interpretation?’), will be treated as a region considered negative by the blinded reader. Otherwise, no imputation for missing data will be performed unless explicitly specified. Rules for partial and missing dates for AEs and medications are given in the [Appendices](#).

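### The SAP both imputes missing histopathology as positive and requires an actual result, so the primary sensitivity test has two possible denominators; for post-NAT scans the imputed truth is unsupported

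*SAP*

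**What the plan says.** Two SAP sections fill in the truth standard when it is absent:

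- Section 7.1.2: "patients with missing or invalid histopathology data (standard of truth) will be imputed as positive for the primary region of interest". The reason given is that PDAC is required for inclusion.
- Section 9.4: such patients "will be considered positive for the primary region of interest", for the same reason.

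Three places require a real result:

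- Section 6.2.1: "only those lesions that have both imaging and histopathology results will be used for primary endpoint calculation".
- Section 7.1.2.1 (EFFS1, the primary analysis set): an interpretable PET result "for at least 1 lesion with a corresponding histopathology result", in both cohorts.
- Section 10.6.2, Table 4 footnote: N is the number of patients who have both the PET and the matching histopathology result.

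Three further provisions matter. SAP 6.2.1 accepts biopsy or resection tissue as the source of the truth standard. SAP 7.1.2.1 and 10.6 score the latest pre-surgery scan, but only for patients who have more than one. The protocol (synopsis, Duration of Participation) places the Cohort 2 core biopsy before NAT and the second scan within 21 days of surgery.

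**The concern.** Read literally, the two sets of rules give different primary analyses. If the EFFS1 definition governs, patients without histopathology are out and the imputation has no effect on the primary endpoint. If the imputation governs, they are in, and the histopathology condition in EFFS1 has no effect. Two analysts could each follow the SAP and report different denominators, and possibly different success decisions.

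The second problem is narrower. Eligibility establishes tumour at entry. Where the scored scan was taken after NAT, the relevant question is whether tumour was still present then, and only the resection specimen answers it. Under the imputation, a PET-positive patient of this kind is counted as a true positive without verification. One whose scan is correctly negative after response is counted as a false negative.

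**Working it through.** **1. Can the passages be reconciled?** They could coexist if a patient entered EFFS1 through a lymph node while the primary lesion's histopathology was missing. SAP Section 8 closes that route: node locations are not recorded in the database, so comparison with histopathology is possible only for the primary lesion. The conflict stands. The SAP does not define when histopathology is invalid, and the imputation is not among the protocol changes listed in Section 8.

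**2. Where does each patient land in Table 4?** Sensitivity = A/(A + C). Suppose the scored scan is post-NAT and no tumour in fact remains.

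| PET | Actual negative histology | Imputed positive |
|---|---|---|
| Positive | B, outside the sensitivity denominator | A, raises sensitivity |
| Negative | D, outside the sensitivity denominator | C, lowers sensitivity |

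For a treatment-naive scan in a patient with biopsy-proven PDAC, imputation and the entry biopsy give the same cell.

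**3. The plan's own power figure.** Inputs from SAP 6.1.2: "an upper one-sided significance level of 0.05", "PG = 0.75 for sensitivity", "True Sensitivity = 0.90", N = 60. Statistic: z = (x/n − 0.75)/√(0.75 × 0.25/n), success if z ≥ 1.645.

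- At n = 60, the standard error is √(0.1875/60) = 0.0559. The cut-off is 60 × (0.75 + 1.645 × 0.0559) = 50.5, so 51 PET-positive patients are needed.
- P(Bin(60, 0.90) ≥ 51) = 92.7%, which reproduces the stated figure. P(Bin(60, 0.75) ≥ 51) = 4.5%.

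**4. How few imputed patients can change the decision?**

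| Verified only | With imputed patients |
|---|---|
| 50/59: z = 1.73, p = 0.042, success | plus 1 PET-negative, 50/60: z = 1.49, p = 0.068, failure |
| 48/57: z = 1.61, p = 0.054, failure | plus 3 PET-positive, 51/60: z = 1.79, p = 0.037, success |

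**5. Range over what is unknown.** The documents give neither the number imputed (m) nor their PET-positive rate (q), so both are assumptions. With s the sensitivity in verified patients, P(success) = P(Bin(60 − m, s) + Bin(m, q) ≥ 51).

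| s | m | q = 0.5 | q = 0.75 | q = 0.9 | q = 1.0 |
|---|---|---|---|---|---|
| 0.75 | 3 | 2.7% | 4.5% | 5.8% | 6.8% |
| 0.75 | 6 | 1.6% | 4.5% | 7.5% | 10.1% |
| 0.75 | 12 | 0.5% | 4.5% | 11.9% | 20.5% |
| 0.90 | 6 | 68.1% | 85.6% | 92.7% | 96.0% |

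When q equals s, nothing changes. The shift can go either way.

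**6. Power if patients without histopathology are dropped and not replaced** (true sensitivity 0.90, same z-test):

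| Verified n | Cut-off | Exact power | Normal approximation |
|---|---|---|---|
| 57 | 49 | 88.8% | 91.9% |
| 54 | 46 | 91.4% | 90.3% |
| 48 | 41 | 89.8% | 86.2% |
| 42 | 37 | 76.0% | 80.7% |

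The exact values do not fall steadily because the cut-off is a whole number; exact alpha across these rows runs from 3.1% to 6.1%.

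**The case against.** The imputation has a sensible basis for most patients. Everyone entered with pathologically confirmed PDAC (Protocol 6.2.2), and SAP 6.2.1 accepts biopsy tissue. For Cohort 1, and for Cohort 2 patients scored on their first scan, entry status is the relevant truth, and replacing the imputation with the biopsy result leaves the Table 4 cell unchanged. This stands, and it confines the bias argument to post-NAT scans.

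A reader might infer that all of Cohort 2 is scored after NAT. The SAP does not say so: the latest-scan rule applies only to patients with several scans. Because the second scan is tied to planned surgery, a patient who never becomes a surgical candidate would usually have only the first.

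A reader might also infer that the imputation is redundant because every patient has a usable biopsy. Protocol 6.1 foresees Cohort 2 participants without a core biopsy before NAT, so this is not established.

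A different PET-positive rate among imputed patients is not in itself bias. If they truly have tumour, counting them is correct; bias requires that tumour be absent. The table in step 5 therefore shows how far the decision can depend on these patients, not an established error rate.

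There is also some transparency already. SAP 10.6.2 lists PET and histopathology results with an EFFS1 identifier, and SAP 10.1 lists reasons for exclusion. A listing does not settle which denominator is primary.

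**Conclusion.** The conflict over the primary denominator is real and follows from the text alone. It should be fixed before the primary analysis is run. The further claim, that the imputed truth is unsupported, holds only for Cohort 2 patients scored on a post-NAT scan without valid resection histology.

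One to three imputed patients are enough to reverse the decision when the result lies near the cut-off. With 6 imputed patients and a verified sensitivity of 0.75, the chance of success runs from 4.5% to 10.1% as their PET-positive rate goes from 0.75 to 1.0. These figures rest on assumed counts and rates, and they apply only if the imputation overrides EFFS1.

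A reader might conclude that the primary result will be inflated. The documents do not support that: the direction depends on the PET results of the imputed patients, and their number is not given. In the text available, no analysis restricted to verified patients is described. The Per Protocol set is a subset of EFFS1, and Section 10 assigns no analysis to it.

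**What to change.** - Remove the imputation from the primary analysis in SAP 7.1.2 and 9.4, and base that analysis on EFFS1 as defined.
- State that the histopathology result must match the scored scan. The entry biopsy counts where that scan is pre-treatment, as SAP 6.2.1 permits; resection histology is required where it is post-NAT. The latest-scan rule stays, so that specimen availability does not choose which scan is scored.
- Define invalid histopathology.
- Keep impute-as-positive as a labelled sensitivity analysis.
- Report the number imputed by cohort, scan and PET result.
- Add the resolved rule to SAP Section 8.

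The cost is SAP wording and one additional table. The primary denominator becomes somewhat smaller, with the loss of power shown in step 6, and post-NAT patients without valid resection histology drop out, which tilts the primary set towards operated patients. The sensitivity analysis shows whether that matters.
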